Chief Investigator: [name]

Co-investigators: [name]

Study Site

The study will take place at Hammersmith and St Mary's Hospitals, London – part of the Imperial College Healthcare NHS Trust.

Study Coordination Centre

For general queries, supply of study documentation, and collection of data, please contact:

Study Coordinator: [name]

Position: Professor of Infectious Diseases

Address: Section of Adult Infectious Disease, Imperial College London, Hammersmith Campus, [name]

[contact]

E-mail: [contact]

Clinical Queries

Clinical queries should be directed to [name] who will answer or direct the query to the appropriate person.

Sponsor

Imperial College London is the research sponsor for this study. For further information regarding the sponsorship conditions, please contact the Head of Research Governance and Integrity ([name]) at:

Head of Research Governance and Integrity [name]

[name]

[name]

[name]

[name]

[contact]

Funder

The Medical Research Council (MRC) has provided funding for this study, in conjunction with Glaxo Smith Kline (GSK). This protocol describes the above study and provides information about procedures for entering participants. Every care was taken in its drafting, but corrections or amendments may be necessary. These will be circulated to investigators in the study. Problems relating to this study should be referred, in the first instance, to the Chief Investigator.

This study will adhere to the principles outlined in the UK policy framework for health and social care research (Version 3.3, 01/11/17). It will be conducted in compliance with the protocol, the Data

Protection Act and other regulatory requirements as appropriate including Good Clinical Practice (GCP).

STUDY SUMMARY

TITLE	Adaptive immunity in older adults infected with respiratory syncytial virus
DESIGN	Human viral challenge study in healthy older volunteers
AIMS	
 1. To test the hypothesis that immune (especially T cell) responses to RSV are quantitatively and qualitatively impaired with aging 2. To identify the mechanisms underlying reduced antigen-specific cell-mediated immunity (CMI) to RSV by comparing the phenotypic and transcriptional changes in T-cells following experimental challenge with RSV in healthy older adults with young adult volunteers.
POPULATION	Healthy persons aged 18 to 40 years and 60 to 75 years. Up to 42 subjects in total

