Based on pilot data from Cherukuri et al., we calculate that a sample size of 8 in each arm would be sufficient to find a difference of 267 SFU/10⁶ between RSV-specific interferon- γ T cell counts by ELISpot in blood, with 80% power using a 2-sided unpaired t-test with 5% significance level (where the variability in each group is 130). Previous data from de Bree et al. studied epitope-specific T cells detected by tetramer that was normally distributed with standard deviation 0.0338. If the true difference in the experimental and control means is 0.0528 as their data indicated, we would need to study 8 experimental subjects and 8 control subjects to be able to reject the null hypothesis with a type I error probability of 0.05. However, tetramer technology (which we are using to mark RSV-specific T cells) depends on matching of certain cell surface markers known as Human Leukocyte Antigen (HLA). Only a proportion of the population have each type of HLA, so not all participants will be suitable for tracking with all tetramers. We therefore aim to recruit 32 volunteers to each group in order to obtain at least 8 individuals with each HLA type required for tetramer labelling. T cell numbers will be compared between young and elderly cohorts using an unpaired t-test (if normality of the T cell distribution, or its transformation, is satisfactory as assessed by histogram with q-qplot and Shapiro-Wilks test) or a Mann-Whitney test (if normality is not satisfactory).

We will perform gene expression analysis on each of 6 patients prior to inoculation and at 3 post-baseline time points. Our main analysis will identify differentially expressed genes between young and elderly adults at each post-baseline time point. The sample size, calculated using the size package from bioconductor which provides pilot data of gene expression variability from the U95 package, predicts that 6 individuals in each group will give us 80% power to detect a potential fold change of 3 in up to 67% of the genes with a Bonferroni multiple testing correction with a genome-wide 5% significance level.

Quantitative assessments of symptom scores, lung function, virus load, leukocyte numbers and inflammatory markers will be compared within subjects to determine differences between baseline

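### The main gene-expression test compares age groups after inoculation and gives the pre-inoculation sample no stated role, so it can mix resting age differences with differences in response to RSV

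*Combined protocol and SAP*

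**What the plan says.** Aim 2 in the Study Summary is to find the mechanisms of reduced cell-mediated immunity by "comparing the phenotypic and transcriptional changes in T-cells following experimental challenge with RSV in healthy older adults with young adult volunteers". The object of interest is a change.

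The Statistics and Data Analysis section gives the sampling as "We will perform gene expression analysis on each of 6 patients prior to inoculation and at 3 post-baseline time points". It then defines the main test: "Our main analysis will identify differentially expressed genes between young and elderly adults at each post-baseline time point". The sample-size statement is a between-group calculation: it "predicts that 6 individuals in each group will give us 80% power". The effect sought is a 3-fold difference, said to be detectable for as many as 67% of genes, and the level is 5% over the genome after Bonferroni adjustment.

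The same section goes on to plan within-subject comparisons of baseline with the infection period. These cover symptom scores, lung function, virus load, leukocyte numbers and inflammatory markers. Gene expression is not listed.

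Section 1.1 (the paragraph on aging and immune senescence) says that immune responsiveness declines and immune regulation alters with age, independently of any challenge. Section 1.5 places the comparison of old with young among the exploratory objectives. The primary objective (section 1.3) is safety and tolerability.

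**The concern.** For any gene, the old-minus-young difference after inoculation is the sum of two parts: the difference that already existed at rest, and the difference in response to RSV. Aim 2 asks about the second part. The stated contrast tests the sum.

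The groups are defined by age, not randomised, so nothing in the design makes the first part zero, and the protocol's own background gives reason to expect that it often is not. A gene that differs at rest and responds identically can be listed as differentially expressed at all three times. A gene with a real response difference opposite in sign to its resting difference can be missed. A reader of the gene list could not tell these apart from the main test alone, although the sample that separates them is taken.

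**Working it through.** **The plan's own figure.** The 6 per group can be neither confirmed nor refuted. The documents give the fold change (3), power (80%), n (6 per group) and genome-wide level (5%). They do not give the number of genes G, the gene-wise SDs, the within-person correlation ρ or the sidedness. I assume G from 5,000 to 50,000 and two-sided t-tests on log2 expression, and solve for the SD that makes the stated 80% true.

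- Effect: δ = log2(3) = 1.585. Level per gene: α = 0.05/G.
- Noncentrality: λ = δ / (σ√(2/6)). Power = P(noncentral t with 10 df and noncentrality λ exceeds t(1−α/2, 10)).
- For G = 10,000: α = 0.000005, critical value 8.81. Power of 80% needs λ = 10.42, so σ = 1.585 / (10.42 × 0.577) = 0.263.
- For G = 5,000, 20,000 and 50,000, σ = 0.284, 0.245 and 0.222.

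The rest follows this gene at the 80% limit.

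**Flag rate with an identical response in both groups.** Let the resting age ratio be R, so that the stated contrast has expectation log2(R). With G = 10,000:

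| Resting ratio R | log2(R) | λ = log2(R)/(0.263 × 0.577) | Flagged at each time |
|---|---|---|---|
| 1.5 | 0.585 | 3.85 | 1% |
| 2 | 1 | 6.58 | 18% |
| 3 | 1.585 | 10.42 | 80% |
| 4 | 2 | 13.15 | 98% |

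Over G = 5,000 to 50,000 the 2-fold figure runs from 19% to 17%, and the others stay at about 1%, 80% and 98%. A test of change has expectation zero for this gene and flags it only at α. A simulation (100,000 replicates, R = 3, ρ = 0.5 and 0.7) agrees: the post-inoculation test flags it 80% of the time, and the change test rejects 5.0% of the time at a nominal 5%.

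**Masking.** If old/young is 1/3 at rest and the response multiplies that ratio by 3, the post-inoculation contrast is log2(1/3) + log2(3) = 0. A 3-fold response difference is then found only at the false-positive rate.

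**Power of the change contrast.** With equal variances before and after, SD(change) = σ√(2(1−ρ)). For a 3-fold difference in change, 6 v 6, G = 10,000:

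| ρ | SD(change) | Power, Bonferroni over genes | Power, Bonferroni over genes × 3 times |
|---|---|---|---|
| 0 | 0.373 | 30% | 17% |
| 0.3 | 0.312 | 55% | 37% |
| 0.5 | 0.263 | 80% | 63% |
| 0.7 | 0.204 | 98% | 93% |

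These move by no more than about 2 percentage points over the range of G. Correcting the level contrast itself for three times also takes it from 80% to 63%, because at ρ = 0.5 the two contrasts have the same SD.

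**The case against.** **Silence is not exclusion.** The section gives one sentence on the main analysis and names no model. The sponsor may intend a model that uses the pre-inoculation sample. A reader might infer that the plan discards that sample; the text supports only that it assigns it no role in the main test. What stands is that the stated contrast, followed literally, is between groups after inoculation, is sized as 6 v 6, and is not supplemented by the within-subject list.

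**The data can still answer the question.** A flagged gene can be checked against its own baseline. That is true, so the weakness lies in the designated test and not in what the study could show. But choosing the contrast after seeing the results is what a plan should prevent.

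**The comparison is exploratory.** This stands, and limits severity. It is also an inference that this analysis serves Aim 2: the aim speaks of T cells, while the statistics section names no tissue and Table 1 lists whole-blood RNA among several sample types.

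**Multiplicity.** A reader might infer that the genome-wide 5% fails across the three times, with 1 − 0.95³ = 14.3% as the true error rate. The documents do not support that. They do not say whether the correction covers time points, control at each time is defensible in exploratory work, and 14.3% assumes independent families whereas the same people are sampled each time.

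**Conclusion.** The point holds as a should-fix. As written, the main test estimates the resting age difference plus the difference in response, while the aim concerns the response. The consequence is conditional: only genes that differ at rest are affected, and for a gene at the plan's own 80% limit the false attribution at each time is about 1% for a 1.5-fold resting difference and becomes large only at about 2-fold (18%) and above (80% at 3-fold, 98% at 4-fold).

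A reader might infer that the gene list will consist mainly of constitutive age differences. The documents give no resting differences, so that is not supported. Nor is any effect on the safety conclusions. The figures rest on my assumptions of 5,000 to 50,000 genes, equal variances over time, normal log2 expression and two-sided tests.

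**What to change.** 1. Define the main contrast as the between-group difference in change from the pre-inoculation sample at each later time: age-by-time terms in a linear model with a participant effect. Change is safer than adjusting for baseline as a covariate, because the groups are not randomised. With slope ρ, covariate adjustment leaves (1−ρ) of the resting difference in the contrast, or 30% of it at ρ = 0.7.
2. Report the pre-inoculation age contrast separately, as the resting age signature.
3. Rerun the 67% power statement for the change contrast, stating the number of genes, the SD source and an assumed ρ.
4. State whether Bonferroni covers the three times. Covering them is optional here.

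No new samples or assays are needed for the change of contrast. The cost is power when ρ is below 0.5: about 55% at 0.3 for the gene above, where 7 per group would be needed for 80%. If the three times are also covered, power is about 37%, 63% and 93% at ρ = 0.3, 0.5 and 0.7. The rerun may therefore show that six per group supports fewer genes than stated.

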Based on extensive preclinical and clinical research, we hypothesise that severe RSV disease (particularly in the setting of older age and pre-existing airways disease such as chronic obstructive pulmonary disease (COPD)) represents a dysregulated and over-exuberant inflammatory response to infection. Steroids have limited efficacy, and identification of druggable inflammatory pathways in severe RSV disease would be of great potential value. A number of promising clinical assets are ready for investigation, however, our ability to test novel therapeutics is limited by the currently available models of viral disease and clinical endpoints tied to disease processes. Observational studies of natural infection are constrained by sampling, timing and access. We therefore propose to extend the experimental human RSV infection studies established at Imperial College to investigate the pulmonary response to RSV infection in older adults, with the development of novel clinical endpoints which can then be used to evaluate the possible impact of treatment with validated novel anti-inflammatory agents in human RSV disease.

Safety of experimental human infections with RSV Since 2010, we have been conducting experimental human challenge studies in volunteers aged between 18 and 55. To date, 61 individuals have been inoculated safely, with around 55% subsequently developing PCR-confirmed infection. Of those, around 66% develop symptoms consistent with a common cold. The infections have been uniformly mild, self-limiting and there have been no serious adverse events.

Challenge studies overcome the many difficulties associated with studying a naturally infected patient group where diagnosis is often delayed; the timing and dose of inoculating virus is extremely variable;

many patients have underlying medical conditions influencing their immune responses; and where they may be subject to therapeutic measures that alter those responses. Using a well-characterised, fully virulent GMP-certified challenge strain of RSV will allow us to closely replicate natural infection but also provide us with the control required to answer important questions about the essential immune responses required for protection and which of these may be impaired with increasing age.

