At the end of the quarantine period (Day 10 post-inoculation) of Group 4, a safety review of the first 10 participants will be carried out to assess the extent of expected and unexpected adverse events, viral shedding and symptom scores. If at least 4 subjects are infected (as defined by PCR detection of virus on at least 2 consecutive days) and none of the infected subjects exhibit any safety concerns (that would trigger a pausing rule), the investigators will discuss the feasibility of intensifying the sampling regime, for example with the addition of bronchoscopy. If less than 4 subjects are infected in the first 10 challenge participants, the pilot study will continue with no intensification of sampling (i.e. no bronchoscopy). A further interim analysis will be performed after the Day 28 post-infection time-point of the first 10 participants. The remaining participants will be challenged in groups as follows:

5. Group 5 (n=5, aged 60-67)
6. Group 6 (n=5, aged 68-75)

The last interim analysis will be performed after the Day 28 post-infection time-point of Group 6 for assessment of attack rate, symptom scores and viral load. A minimum of 4 infected subjects without safety concerns in the first cohort supports a probability of at least 80% for the absence of safety concerns in the next 5 infected subjects from the second cohort. Prior to the first cohort, we assume a probability of 50% or more for the absence of safety concerns in the first Group of 4 or 5 infected subjects, based on our experience in younger subjects. The calculations assume, prior to the first cohort, a 95% credible interval for the probability of safety concerns covering a range between 0% and 97% and centred around 27.5%. Prior to the second cohort, assuming at least 4 infected subjects and no safety concern, the 95% credible interval would cover a range between 0% and 34% and centred around 5.5%. The probability of an absence of safety concerns in a Group 4 or 5 subjects is calculated using a beta-binomial distribution with parameters 0.275 and 0.725 prior to the first cohort, and 0.275 and 4.725 prior to the second cohort. The probability of no event in 4 or 5 subjects from those distributions are equal to ~50% and ~80% respectively prior to the first and prior to the second cohort.

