1.12. Withdrawal criteria

Any subjects can withdraw from the study at any time if they wish to. Subjects can also be removed from the study if an investigator feels this is necessary or appropriate. Subjects will be closely monitored throughout by the study doctor. This is defined further in the section on 'Serious Adverse Events'.

If a participant loses capacity during the study, the participant would be withdrawn from the study. Identifiable data or tissue already collected with consent would be retained and used in the study. No further data or tissue would be collected, or any other research procedures carried out on or in relation to the participant.

Table 1: Study procedures

Procedures	DAY (relative to viral inoculation)																			
	Screen	-14	0	1	2	3	4	5	6	7	8	9	10	11	12	13	14	28	166	180
Time window (days)	≤ -90	±7															±1	±7	±7&	±14
Consent	X																			
Physical Examination	X	X	X														X	X		X
Chest X-Ray	X																			
12 lead ECG	X			X		X		X		X		X								
Lung Function Tests	X	X	X	X	X	X	X	X	X	X	X	X					X**	X		X
Safety bloods	X																			X
Screening urine tests	X																			
Blood - serum			10															10		10
Blood - PBMCs (mls)		40	50	10***	10***	10***					60*		60					20	60	60
Blood – plasma (mls)	4		4	4	4	4	(4)	()	(4)	4	(4)	(4)	4					4	4	4
Blood – RNA (mls)		6	6	6	6	6	(6)	(6)	(6)	6	(6)	(6)	6					6	6	6
Oral swab			X	X	X	X	X	X	X	X	X	X	X				X	X		X
Throat swab X 2	X	X	X	X	X	X	X	X	X	X	X	X	X					X		
Stool swab X 2			X	X	X	X	X	X	X	X	X	X	X							
Nasal lavage (daily)	X	X	X	X	X	X	X	X	X	X	X	X	X	(X)	(X)	(X)	X	X		X
Nasosorption (SAM)	X	X	X2	X	X	X	X	X	X	X	X	X	X				X	X2		X
Nasal scrape (Rhinopro®)	X	X		X	X	X				X			X				X	X		X
Nasal brushing		X																		X
Bronchoscopy(*):		X									X*							X		X
Virus inoculation			X																	
Symptom diary check			X	X	X	X	X	X	X	X	X	X	X	X	X	X	X	X		
Collect symptom diaries																	X			

(*) Bronchoscopy includes: Bronchosorption using SAM (4)
Bronchial biopsy (8), Bronchial brush (4) and Bronchoalveolar lavage (BAL),
(number): the blood collection on days 4, 5, 6, 8 and 9 are optional and will be collected or collection withheld at the investigator's discretion (plasma and RNA).

*Second bronchoscopy will take place on Day 7 post-inoculation at the earliest and at Day 9 post-inoculation at the latest. PBMCs will be collected on the same day as the bronchoscopy.

** Optional if normal spirometry throughout quarantine period

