1.24.2. Potential adverse events of bronchoscopy

Bronchoscopy is a safe procedure, with serious complications occurring in less than 1 in 1000 procedures. It is frequently performed on patients with lung diseases such as asthma, and even in critically-ill and frail elderly patients. The bronchoscopy may cause cough for a few hours, and there may be some discomfort during the procedure, but this is reduced with local anaesthetic and sedation.. The sedation makes participants drowsy, but this usually wears off after a few hours. Participants should not drink alcohol after receiving sedation. Minor bleeding caused by irritation of the airways from the telescope may occur (less than 1 in 100), but this does not require treatment. Serious bleeding requiring treatment is very rare (less than 1 in 1000). The fluid used to wash the airways (lavage) can cause some irritation, which manifests as a brief fever in 10-30% of cases. This is self-limiting and can be treated with paracetamol. On rare occasions the airways can narrow – if this occurs medication can be given to open the airways. Occasionally after taking the tissue sample (biopsy) people can cough up small amounts of blood but this will stop without further treatment. Very rarely (less than 1 in 1000), the lung can collapse (pneumothorax) after bronchial biopsy; we would arrange for all necessary treatment in the unlikely event should this occur.

Bronchosorption is likely to have less adverse effects than bronchoalveolar lavage, brushing and biopsy (the standard bronchoscopy tools) as it should not cause bleeding, infection or a reactive pyrexia. The only additional adverse event relating specifically to bronchosorption is dislodgement of the SAM from the forceps. If this does occur the SAM can be retrieved using standard endobronchial forceps and snares available routinely in the bronchoscopy suite.

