and during infection. Intra-subject differences will be analysed using ANOVA and 2-tailed paired Student's t-tests or Wilcoxon signed rank test as appropriate. Correlations between inflammatory cell, illness severity, viral load and leukocyte counts will be examined using Spearman's rank correlations to investigate possible causal relationships.

Data and all appropriate documentation will be stored for a minimum of 10 years after the completion of the study, including the follow-up period according to Imperial College London policy.

REGULATORY ISSUES

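### For lung function, leukocytes and inflammatory markers, infection-period values are tested only against own baseline, so procedure effects cannot be separated from RSV effects; challenged but uninfected participants could serve as a comparator

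*Combined protocol and SAP*

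**What the plan says.** The section Statistics and Data Analysis lists symptom scores, lung function, "virus load, leukocyte numbers and inflammatory markers will be compared within subjects to determine differences between baseline" and the infection period. The method is given in one sentence: "Intra-subject differences will be analysed using ANOVA and 2-tailed paired Student's t-tests or Wilcoxon signed rank test as appropriate". No significance level is stated for these tests, and the section does not say whether participants who never become infected are included in them. The other planned analyses are young-versus-elderly comparisons of T cells and gene expression, and Spearman correlations that include viral load. No section compares infected with uninfected participants, and there is no sham-inoculated or procedure-only group.

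Table 1 schedules nasal lavage and nasosorption daily on Days 0 to 10 and nasal scrapes on Days 1, 2, 3, 7 and 10. Its footnote says "Second bronchoscopy will take place on Day 7 post-inoculation at the earliest and at Day 9 post-inoculation at the latest". Sections 1.17 to 1.17.4 describe that procedure as sedated, with up to eight biopsies, four brushings and a lavage of 180 to 240 ml. Section 1.24.2 says lavage can cause irritation, "which manifests as a brief fever in 10-30% of cases".

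Two safeguards exist. Section 1.16 puts nasal procedures before a same-day bronchoscopy. Section 1.22 measures the effect of the first bronchoscopy on the symptom diary and subtracts it where appropriate, and has symptoms recorded before that day's procedures.

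On infection, section 1.1 reports "To date, 61 individuals have been inoculated safely, with around 55% subsequently developing PCR-confirmed infection", in volunteers aged 18 to 55. Section 1.6 has a working definition of infected: "as defined by PCR detection of virus on at least 2 consecutive days".

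**The concern.** A paired test asks whether a marker moved. It does not ask why. Here the virus and the sampling burden begin together on Day 0, and in the main study an invasive airway procedure is added on Day 7 to 9. If daily nasal sampling, or the bronchoscopy for samples taken after it, moves a marker, the own-baseline contrast counts that movement together with any effect of RSV.

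The protocol treats this as a real possibility for symptoms and for nasal samples, since it has provisions for both. It has none for lung function, leukocyte numbers or inflammatory markers, and none for repeated nasal sampling on any outcome. Section 1.1 hopes that the work will yield new clinical endpoints for testing anti-inflammatory agents. A marker that partly reflects the sampling would be a poor candidate. Meanwhile the trial is expected to produce many challenged, uninfected participants on largely the same schedule, and the plan gives them no role.

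**Working it through.** The plan gives no sample size, effect size, SD or power for the within-subject analysis, so it has no figure to reproduce.

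**Step 1. Which samples can be affected by which procedure**

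| Data (Table 1) | Nasal procedures | In-quarantine bronchoscopy |
|---|---|---|
| Samples on Days 1 to 6 | Yes, daily | No, it comes later |
| Nasal samples on the bronchoscopy day | Yes | No, taken first (section 1.16) |
| Blood on the bronchoscopy day | Yes | Unclear: PBMCs are drawn the same day, order not stated |
| Lung function, scheduled Days 0 to 9 | Yes | Only for a test after a Day 7 to 9 bronchoscopy |
| Day 10 PBMCs, plasma and RNA | Yes | Yes, 1 to 3 days afterwards |

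**Step 2. Expected numbers**

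Inputs: attack rate 55% (section 1.1); up to 42 participants, 30 older and 12 young (study summary, section 1.8).

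- All 42: 0.55 × 42 = 23.1 infected and 0.45 × 42 = 18.9 uninfected. The 95% binomial range for uninfected is 13 to 25.
- The 30 older: 16.5 infected and 13.5 uninfected (range 8 to 19).
- The 12 young: 6.6 infected and 5.4 uninfected.
- If none of the up to 20 pilot participants has a bronchoscopy, 42 − 20 = 22 do: 0.55 × 22 = 12.1 infected and 9.9 uninfected. The 22 is inferred; section 1.6 allows bronchoscopy to be considered after the first 10.

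Attack rates of 40% and 70% (assumed) would leave about 25 and 13 uninfected of 42.

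**Step 3. Paired test with a procedure shift and no RSV effect**

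Let d be the shift divided by the SD of the within-subject change. The paired t statistic is noncentral t with n − 1 degrees of freedom and noncentrality d√n. A two-sided 5% level is assumed. The values of d are also assumptions, because the documents give none.

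| n infected | d | d√n | Critical value | P(reject) |
|---|---|---|---|---|
| 12 | 0.25 | 0.87 | 2.20 | 12% |
| 12 | 0.5 | 1.73 | 2.20 | 35% |
| 23 | 0.25 | 1.20 | 2.07 | 21% |
| 23 | 0.3 | 1.44 | 2.07 | 28% |
| 23 | 0.5 | 2.40 | 2.07 | 63% |
| 23 | 0.8 | 3.84 | 2.07 | 96% |

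A simulation of 20,000 trials with n = 23 gave 28%, 63% and 96% at 0.3, 0.5 and 0.8 SD.

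**Step 4. Change compared between infected and uninfected**

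t = (mean change in infected − mean change in uninfected) / (s√(1/n1 + 1/n2)). A shift common to both groups drops out of the numerator. In the same simulation (23 v 19), rejection was 4.8%, 4.9% and 5.2% at shifts of 0.3, 0.5 and 0.8 SD.

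**Step 5. Precision of that comparison**

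Difference in change detectable with 80% power, two-sided 5%, unadjusted:

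- 23 v 19 (all): 0.89 SD
- 17 v 13 (older): 1.07 SD
- 12 v 10 (the inferred 22): 1.26 SD
- 7 v 5 (young): 1.82 SD

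A paired test in 12 participants detects 0.89 SD with 80% power. At 0.89 SD the 12 v 10 comparison has 51% power.

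**The case against.** The strongest reply is that no harm has been shown. The documents give no procedure effect on FEV1, leukocytes or any inflammatory marker, and fever after lavage is not among the listed outcomes. Step 3 puts a shift in and finds it again. That stands. A reader might infer that the paired tests will turn significant even without an RSV effect; the documents support only that such a result could not be attributed.

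A reader might also infer that bronchoscopy contaminates the whole infection window. It does not, as Step 1 shows. Nor is baseline free of procedures: nasal lavage and nasosorption are also done at screening, Day −14 and Day 0, and bronchial samples are compared with earlier bronchial samples. Daily repetition is what is new after inoculation. Virus load is in the quoted list, but the procedures do not plausibly produce challenge virus.

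The uninfected are not a clean control either. Infection status is not randomised. Section 1.1 links low nasal IgA to susceptibility and suggests an early-defence role for resident memory T cells, so the groups may differ in prior immunity, and some of the uninfected may have had an abortive infection. Schedules are similar but not identical: bronchoscopy day, some blood draws and discharge day vary. With the loss of power in Step 5, this argues against replacing the paired tests. It does not argue against adding the comparison.

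Finally, safety is the primary objective and the comparative objective is young versus elderly. In that contrast a shift equal in both age groups cancels, and a constant shift cannot create a correlation with viral load. Both points are correct and limit the consequences, but neither analysis tests whether RSV changed a marker.

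**Conclusion.** The point holds for lung function, leukocyte numbers and inflammatory markers. The plan's only test of change during infection cannot tell an RSV effect from an effect of repeated nasal sampling on Days 0 to 10, or of the Day 7 to 9 bronchoscopy for later samples such as Day 10 blood. Symptom scores are partly protected: the correction covers bronchoscopy only and has no rule for when it applies. Virus load is outside the point.

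The structural gap does not depend on any assumed number, but its practical size does. The rejection rates of 21% to 63% with 23 infected rest on assumed shifts of 0.25 to 0.5 SD, a 5% two-sided level, and an attack rate observed at ages 18 to 55. The documents do not show that such shifts occur. About 19 of 42 challenged participants are expected to be available as a comparator, imperfect but already sampled.

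**What to change.** 1. Keep the paired tests, and restrict the infection-period tests to participants who meet the PCR definition in section 1.6. State this in the statistics section.
2. Add a prespecified comparison of change from baseline between PCR-infected and challenged PCR-negative participants who had the same procedures, adjusted for baseline value and age cohort, or rank-based if the data are not normal. For samples taken after a bronchoscopy, compare only participants who had one. Report the estimate with its confidence interval.
3. Attribute a change to RSV only when this comparison supports it. Otherwise describe it as a change after challenge and procedures.
4. State that blood on the Day 7 to 9 bronchoscopy day is drawn before the procedure, and label Day 10 results as post-bronchoscopy where one was done. The nasal order is already set.
5. State the limits: infection status is not randomised, the uninfected may differ in prior immunity or have had an abortive infection, and 80% power is reached only at about 0.89 SD (23 v 19) or 1.26 SD (12 v 10).

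The cost is analysis wording and one line on blood order; no extra participants or samples are needed. The price is precision: a real but moderate RSV effect may go unattributed, and an inconclusive comparison must not be read as evidence that the procedures caused the change.
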